7.2.1.2. Sensitivity Analysis

A sensitivity analysis will be performed on the primary efficacy endpoint. For this analysis, participants who dropped out of the study prior to reaching Day 14 after IEC without experiencing any CRS event of \geq Grade 2 will be excluded. If there is no participant in this situation, the sensitivity analysis will not be performed. The same method for the primary efficacy endpoint analysis specified in Section 7.2.1 will be used for this analysis, except that no hypothesis testing will be conducted here.

7.2.1.3. Supportive Analysis

A supportive analysis will be conducted by comparing the itacitinib 200 mg QD dose in Part 1 with the placebo group in Part 2, using a 95% CI (2-sided), for participants with B-cell lymphoma and treated with Yescarta as the IEC therapy. For the itacitinib 200 mg QD treatment group, only participants with B-cell lymphoma and treated with Yescarta from Part 1 will be considered; whereas all participants in the placebo treatment group from Part 2 are considered for this analysis. This analysis is performed in the same way as the primary efficacy endpoint analysis for Part 2, except that no hypothesis testing is conducted.

As another supportive analysis, comparison between the itacitinib 200 mg QD dose from Part 1 and the itacitinib 200 mg BID treatment group from Part 2 will be conducted in the same way as the analysis specified above, for participants with B-cell lymphoma and treated with Yescarta as the IEC therapy, except that no hypothesis testing is conducted.

7.3. Analysis of the Secondary Efficacy Parameters

7.3.1. Immune Effector Cell-Associated Neurotoxicity Syndrome Incidence

Incidence of ICANS, defined as the percentage of participants experiencing ICANS by Day 28 (over the first 28-day period) after IEC therapy, will be summarized and presented together with its exact 95% CI (2-sided). The 95% CIs will be calculated in the same way as for the CRS rate in Section [7.2.1](#).

There will be no missing data imputation in calculation of ICE score or ICANS grading. In addition, ICANS incidence will be provided separately for each IEC therapy.

7.3.2. Onset and Duration of Immune Effector Cell-Associated Neurotoxicity Syndrome

Time to first onset of ICANS from date of IEC infusion is summarized within the first 28 days. Participants without ICANS will be considered as missing and not included in the summary.

The duration of ICANS is defined as the number of days where a participant has a non-zero ICANS grade. Duration of ICANS by Day 28 after IEC as the secondary analysis will be summarized. For investigational purpose, duration of all ICANS including events after Day 28 may also be conducted.

For ICANS that occurs prior to or on Day 30, refer to the information collected on the ICANS assessment log of the CRF; for ICANS that occur after Day 30, refer to the information collected on the ICANS page of the CRF.

Summary statistics including mean, median, standard deviation, minimum, and maximum will be provided for time to first onset of ICANS and duration of ICANS.

7.3.3. Onset and Duration of Cytokine Release Syndrome

Time to first onset of CRS from date of IEC infusion will be summarized within the first 28 days. Participants without CRS will be considered as missing in the summary.

Duration of CRS is defined as the number of days where a participant has a CRS event. Duration of multiple occurrence of CRS within each participant will be added together regardless of grading. The duration of CRS by Day 28 as the secondary analysis will be summarized. For investigational purposes, a summary of the overall duration may be conducted..

Summary statistics including mean, median, standard deviation, minimum, and maximum are provided for time to first onset of CRS and duration of CRS by treatment group.

7.3.4. Cytokine Release Syndrome-Free Survival

The CRS-free survival analysis will be performed using the Kaplan-Meier method, with the following events considered as the events of interest:

- CRS of \geq Grade 2
- Death
- Initiation of tocilizumab with the indication of CRS treatment
- Initiation of corticosteroids with the indication of CRS treatment

For participants who experience any of the events of interest mentioned above, the time-to-event variable will be calculated as the number of days from IEC therapy to the first occurrence of the events of interest. For participants who do not experience any of the events of interest, they will be treated as censored observations, and the time-to-event variable will be calculated as the number of days from Day 0 to the date of the last available CRS assessment by Day 28. The numbers of participants who do and do not experience any of the events of interest will be summarized. The median CRS-free survival in days, and the CRS-free survival rates on Days 7, 14, 21, and 28 will be included in the summary.

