6.4.2. Restricted Medications and Procedures

The following medications have restrictions on use during the treatment period of the study:

- Aspirin in doses exceeding 125 mg per day is not permitted. Low-dose aspirin (≤ 125 mg per day) is permitted unless clinically contraindicated.
- Coadministration with strong CYP3A inhibitors.
 - If the participant's medical condition requires treatment with posaconazole, itraconazole, voriconazole, mibefradil, or clarithromycin, a dose reduction of itacitinib is recommended (see below), as strong CYP3A inhibitors have been shown to increase exposure to itacitinib (see [Appendix B](#)).

Part 1 dose reduction: Itacitinib 200 mg QD may be reduced to 100 mg QD.

Part 2 dose reduction: Itacitinib 200 mg BID (or Placebo) may be reduced to 100 mg BID or placebo.

- The sponsor medical monitor may be consulted for advice when CYP3A inhibitors are considered.
- If concomitant administration of an anticoagulant/antiplatelet medication is indicated, then caution and enhanced monitoring is required. History of thrombocytopenia should be a factor in the choice of anticoagulant and dose.
- Tocilizumab and/or corticosteroids for CRS Grade 1 is not allowed. However, tocilizumab may be given as rescue medication for CRS Grade 1 if no improvement is observed within 72 hours from onset, and the participant's medical condition requires intervention per investigator judgment.

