6.4.3. Prohibited Medications and Procedures

The following medications are prohibited during the treatment period of the study:

- Concomitant use of another JAK inhibitor.
- Initiating therapy with an investigational medication unless otherwise approved by the medical monitor, such as anakinra in the treatment of CRS.
- Coadministration with strong CYP3A inducers. The FDA DDI website provides the most current list of strong CYP3A inducers.

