7.3.7. Intervention for CRS and ICANS

To assess intervention for CRS, the use of tocilizumab and corticosteroid for CRS treatment will be summarized. All use of tocilizumab and corticosteroid are listed including ICANS as the indication.

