1.5 Others		
1.5.1	Summary of General Medical History	Safety
1.5.2	Summary of Death	
2 Efficacy (add subgroup analysis as needed)		
2.1.1	Summary of CRS Rate by Day 14 After IEC Therapy	EAS
2.1.1.1	Sensitivity Analysis: Summary of CRS Rate by Day 14 After IEC Therapy – Excluding Participants Who Drop Out of the Study Prior to Day 14 Without Experiencing \geq Grade 2 CRS	EAS
2.2.1	Summary of ICANS Rate by Day 28 After IEC Therapy	EAS
2.2.2.1	Summary of Onset and Duration of ICANS by Day 28 After IEC Therapy	EAS
2.2.2.2	Summary of Onset and Duration of ICANS During the Lifetime of the Study	EAS
2.2.3.1	Summary of Onset and Duration of CRS by Day 28 After IEC Therapy	EAS
2.2.3.2	Summary of Onset and Duration of CRS During the Lifetime of the Study	EAS
2.2.4.1	Summary of CRS-Free Survival by Day 28 After IEC Therapy	EAS
2.2.4.2	Summary of CRS Rate Within 48 Hours and by Day 28 After IEC Therapy	EAS
2.2.4.3	Summary of Tocilizumab and Corticosteroid Use for CRS Treatment	EAS
[REDACTED]	[REDACTED]	[REDACTED]
[REDACTED]	[REDACTED]	[REDACTED]

Table No.	Title	Population
[REDACTED]	[REDACTED]	[REDACTED]
[REDACTED]	[REDACTED]	E [REDACTED]
[REDACTED]	[REDACTED]	[REDACTED]
[REDACTED]	[REDACTED]	[REDACTED]
Safety		

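### CRS-free survival and the rescue summary count only tocilizumab and corticosteroids, so a participant whose sole CRS rescue is approved anakinra is missed (minor)

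*SAP*

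**What the plan says.** SAP 7.3.4 defines four events for CRS-free survival: CRS of Grade 2 or higher, death, "Initiation of tocilizumab with the indication of CRS treatment" and "Initiation of corticosteroids with the indication of CRS treatment". The list has no term for any other agent. On everyone else the SAP says: "For participants who do not experience any of the events of interest, they will be treated as censored observations". Their time runs to the last available CRS assessment by Day 28.

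SAP 7.3.7 describes the rescue reporting for CRS: "the use of tocilizumab and corticosteroid for CRS treatment will be summarized". SAP Appendix A carries this into Table 2.2.4.3, "Summary of Tocilizumab and Corticosteroid Use for CRS Treatment", and into Listing 2.6.5, whose title names the same two classes. The readable SAP text does not mention anakinra.

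Protocol 6.4.3, under prohibited medications for the treatment period, has the entry "Initiating therapy with an investigational medication unless otherwise approved by the medical monitor, such as anakinra in the treatment of CRS". Protocol 6.4.2 separately restricts rescue at Grade 1: "Tocilizumab and/or corticosteroids for CRS Grade 1 is not allowed". It then gives a conditional exception for tocilizumab.

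**The concern.** The drug events in SAP 7.3.4 do their work mainly below Grade 2, because CRS of Grade 2 or higher is already an event whatever treatment is given. They stop a participant who was treated for Grade 1 CRS from being counted as a success. A closed list of two classes does this only for those two classes, while the protocol itself names a third agent that may be approved for CRS.

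Two participants with the same Grade 1 course could therefore be classified in opposite ways, depending only on which drug was given. In the rescue table, use of anakinra in place of tocilizumab would read as less rescue. Protocol 10.4.2.1 lists rescue medication among the inputs to final dose selection, so the table has a use beyond description.

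**Working it through.** **Scope of the check.** The point concerns event definitions, and the plan gives no figure for it. The nearest stated figure is the Part 2 power of 70% (Protocol 10.1, SAP 3.4). With 23 per arm, 50% versus 20% and one-sided 5%, the pooled Z-test formula gives

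Φ[(0.30·√23 − 1.645·√(2·0.35·0.65)) / √(0.25 + 0.16)] = Φ[(1.439 − 1.110)/0.640] = Φ(0.514) = 69.6%.

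This agrees with 70%. It concerns the primary endpoint, which depends on CRS grade alone and is not touched by this point.

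**Step 1. Apply the SAP rules as written.** Inputs are the events in SAP 7.3.4 and the drugs in SAP 7.3.7 and Table 2.2.4.3. "Anakinra" in the table stands for any approved agent outside the two listed classes.

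| Course by Day 28 | CRS-free survival | Rescue table |
|---|---|---|
| Grade 1, survives, tocilizumab only | Event | Counted |
| Grade 1, survives, anakinra only | Censored | Missing |
| Grade 2 or higher, anakinra only | Event (by grade) | Missing |
| Any grade, anakinra plus tocilizumab or a corticosteroid for CRS | Event | Counted |
| Dies | Event | Depends on the drug given |

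The first two rows differ only in the drug, yet they are classified in opposite ways. Wrong classification as event-free needs all of these: CRS stays at Grade 1, the participant survives, and neither tocilizumab nor a corticosteroid is given for CRS. Absence from the rescue table needs only that the other agent is the sole CRS rescue, at any grade.

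**Step 2. Where the use would still be seen.** SAP 6.6 tabulates all concomitant medications by drug class (Table 1.4.2), and Listing 2.4.6 lists them. Anakinra would appear there. These outputs are not organised by CRS indication and do not feed the composite.

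**Step 3. Size per participant.** Inputs are 23 evaluable per arm in Part 2 and 62 in Part 1 (Protocol 10.1). The shift in the crude proportion is k/n for k such participants:

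- Part 2 arm: 1/23 = 4.3 points, 2/23 = 8.7 points, 3/23 = 13.0 points.
- Part 1 overall: 1/62 = 1.6 points, 2/62 = 3.2 points, 3/62 = 4.8 points.

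The Kaplan-Meier rate at a landmark day moves by the same 1/n if nobody is censored before that day and the rescue began before it. The values of k are assumptions for scale. The documents give no frequency of anakinra use.

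**The case against.** The case for leaving the SAP alone has several good parts.

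- **Anakinra is prohibited by default.** Use needs approval by the medical monitor, and nothing in the documents shows it being approved or used in Grade 1 CRS. The entry can also be read with anakinra as an example of the prohibited class rather than of the exception. This stands as a reason to expect few cases. On either reading an approved agent for CRS is possible, and the SAP has no rule for it.
- **The rescue summary follows the protocol.** The CRS intervention endpoint in Protocol Table 7 and SAP Table 1 is tocilizumab use alone. That is correct, so SAP 7.3.7 does not breach the protocol. But the SAP already goes beyond that endpoint by adding corticosteroids, and the stated objective is intervention for CRS generally.
- **The stakes are low.** CRS-free survival is not among the visible listed endpoints, and SAP 7.3.4 attaches no test or decision rule to it. This stands and sets the severity.

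Some stronger readings are tempting but not supported:

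- *Every participant rescued with anakinra is reported as event-free and unrescued.* The table above shows that this is too broad.
- *The interim rate predicts the size.* Protocol 2.3.3 reports that 2 of 26 participants received tocilizumab for Grade 1 CRS. This shows that rescue at Grade 1 happens. It says nothing about how often a different drug, prohibited by default, would be used.
- *The gap favours itacitinib.* If rescue follows need, the planning rates of 50% and 20% suggest more use on placebo, and the omission would then work against itacitinib. A reader might note that Protocol 4.1 leaves the sponsor unblinded in Part 2 and suspect uneven approval. The documents do not say whether the medical monitor is blinded, and investigators and participants are. The direction is unknown.
- *CRS-free survival is the only analysis that counts rescue as failure.* Redactions in the SAP contents and table list prevent this from being verified.

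**Conclusion.** The gap is real but narrow. Applied as written, SAP 7.3.4 censors as CRS-free a surviving participant with Grade 1 CRS whose only rescue is an approved agent other than tocilizumab or a corticosteroid. SAP 7.3.7 and its outputs omit any participant, at any grade, for whom such an agent is the sole CRS rescue.

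The cost is 4.3 points of one Part 2 arm's crude proportion per participant, or 1.6 points in Part 1. How many participants this would affect cannot be judged from the documents. The conclusion rests on the approval route in Protocol 6.4.3 being usable for CRS treatment, and on the SAP's event list being closed, as it reads. Severity: minor.

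**What to change.** This changes reporting only and leaves the treatment rules as they are.

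1. In SAP 7.3.4, add a fifth event: start of anakinra, or of any other anticytokine or investigational agent, given to treat CRS.
2. Use the same list of agents in SAP 7.3.7, Table 2.2.4.3 and Listing 2.6.5.
3. Keep the tocilizumab-only proportion as its own row in Table 2.2.4.3, so that the protocol endpoint is still reported as defined.
4. Confirm that the CRF records an indication for these agents. The SAP's selection by indication implies this for tocilizumab and corticosteroids, but the CRF is not among the documents.

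The cost is a short wording change and one added selection term in programming. If the indication is recorded, no new data are needed. The CRS-free rate may come out slightly less favourable.

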Hepatitis screening	X													8.3.5.2	
Pregnancy testing	X	X									X	X		8.3.5.1	
Lumbar puncture with paired blood samples ^g	Only if performed based on SOC													—	
Urinalysis	X										X			8.3.5	
CRP	X	X		X	X	X	X	X	X	X	X			8.3.5	
Ferritin levels	X	X		X	X	X	X	X	X	X	X			8.3.5	

ASBMT = Association for Blood and Bone Marrow Transplantation; CRP = C-reactive protein; CRS = cytokine release syndrome; CT = computed tomography;

ECG = electrocardiogram; ECHO = echocardiogram; ECOG = Eastern Cooperative Oncology Group; EOS = end of study; EOT = end of treatment;

FDG-PET = fluorodeoxyglucose positron emission tomography; ICANS = immune effector cell-associated neurotoxicity syndrome; ICE = immune effector cell-associated encephalopathy; IEC = immune effector cell; LDH = lactate dehydrogenase; MRI = magnetic resonance imaging; PBMC = peripheral blood mononuclear cell; PK = pharmacokinetics; SOC = standard of care.

^a Decentralized assessments are acceptable during screening and post-treatment (see Section 11.1).

^b EOT: Treatment will end on Day 26; however, the participant will be assessed at Day 28 ± 2 days. If a participant ends treatment early, an EOT visit should be conducted at the time that the participant discontinues treatment.

^c If hematologic disease assessments are performed at different timepoints, based on institutional guidelines, then this is acceptable. All disease assessments should be captured in the eCRF.

^d CRS will be evaluated at each visit during the study. In addition, participants should be monitored during the study and evaluated for CRS if fever is present.

^e ICANS will be evaluated at each visit during the study. In addition, participants should be monitored during the study and evaluated for ICANS if there are signs and symptoms relating to neurotoxicity.

^f Screening for central laboratory assessments must be performed within 7 days of Day -3. If screening laboratory assessments are performed within 3 days before Day -3, then the tests do not need to be repeated on Day -3. Any laboratory samples collected on Day -3 must be collected before study treatment administration.

^g Lumbar puncture is not required; however, if one is performed per SOC, then it should be captured in the eCRF.

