8.9.4. Survival Follow-Up

Participants will be contacted by telephone, email, or with a visit to assess for survival. All participants will be followed for survival until EOS (Day 180), unless informed consent is withdrawn.

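### SAP 7.3.4 limits censoring to Day 28 but not event times, so late first events can force the CRS-free survival curve to zero and print a false median

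*SAP*

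**What the plan says.** SAP 7.3.4 plans a Kaplan-Meier analysis with four events of interest: CRS of Grade 2 or higher, death, and the start of tocilizumab or of corticosteroids to treat CRS. It has two timing rules.

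- Participants with an event: "the time-to-event variable will be calculated as the number of days from IEC therapy to the first occurrence of the events of interest".
- Participants without any event are censored. Their time is the "number of days from Day 0 to the date of the last available CRS assessment by Day 28".

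The first rule has no upper limit. No rule covers a participant whose first event comes after Day 28. The planned outputs are the median, the rates at Days 7, 14, 21 and 28, and event counts: "The numbers of participants who do and do not experience any of the events of interest will be summarized".

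The neighbouring sections put the window on the events themselves. SAP 7.3.1 counts ICANS "by Day 28 (over the first 28-day period) after IEC therapy". SAP 7.3.2 says: "Time to first onset of ICANS from date of IEC infusion is summarized within the first 28 days". SAP 7.3.3 says: "Time to first onset of CRS from date of IEC infusion will be summarized within the first 28 days".

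Two Protocol statements fix the relevant dates. Table 3, footnote b: "Treatment will end on Day 26; however, the participant will be assessed at Day 28 ± 2 days". Section 8.9.4: "All participants will be followed for survival until EOS (Day 180), unless informed consent is withdrawn". SAP Appendix A also plans a listing of CRS assessments after Day 30 (Listing 2.6.1.2), so late CRS as well as late deaths can be in the database.

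**The concern.** Kaplan-Meier needs events and censoring to be observed over the same period. Here a participant who dies on Day 100 is an event at 100 days, while a participant alive and event-free on Day 100 left the risk set at about Day 28. After the Day 28 assessments, the risk set is therefore selected on the future: it contains only people already known to have an event. The estimate must reach zero at the last of these events, however many participants remained event-free.

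The median, the event count and the part of Figure 4.1.1 after Day 28 would then mislead. The group with fewer early events is the more exposed. Its Day 28 estimate is more likely to be above 50%, and it has more participants who can have a late first event. Side by side, an arm in which prevention worked could show a finite median that reflects only the coding rule.

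**Working it through.** The documents give no figure for CRS-free survival, so there is none to reproduce. The check applies the product-limit formula, S(t) = product of (1 − d/n) over event times, where d is the number of events and n the number at risk.

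**Inputs.** The arm size of 23 is from SAP 3.2. The event and censoring rules are from SAP 7.3.4, and follow-up to Day 180 is from Protocol 8.9.4. The event counts and times are assumptions: 5 first events by Day 9, one death on Day 100, and the other 17 participants event-free and assessed on Day 28.

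**To Day 28.** No one is censored earlier, so S(28) = 18/23 = 0.783 under every rule.

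**After Day 28.**
- As written: 17 participants leave at Day 28. On Day 100, n = 1 and d = 1, so S = 0.783 × (1 − 1/1) = 0.
- Events and censoring both limited to Day 28: the death is not counted, and that participant is censored with the others.
- Events and censoring both followed to Day 180: on Day 100, n = 18 and d = 1, so S = 0.783 × 17/18 = 0.739.

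| Rule | Events | S(28) | S(100) | Median |
|---|---|---|---|---|
| SAP 7.3.4 as written | 6 | 0.783 | 0 | 100 days |
| Both limited to Day 28 | 5 | 0.783 | not estimated | not reached |
| Both followed to Day 180 | 6 | 0.783 | 0.739 | not reached |

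The written rule agrees with neither consistent alternative.

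**Two late events** (assumed Days 60 and 100, 16 censored at Day 28). S(60) = 0.783 × 1/2 = 0.391 and S(100) = 0. The printed median is 60 days.

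**Where no false median arises.**
- No late first event: the curve stays at 0.783.
- Twelve early events of 23: S(28) = 11/23 = 0.478, so the median is reached by Day 28 and is the same under the written and the 28-day rule.
- First event on Day 29 while 6 participants are censored on Day 30, if the visit window counts as by Day 28: n = 7, and S = 0.783 × 6/7 = 0.671.

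**How often.** With 18 participants event-free at Day 28, the chance of at least one late first event is 1 − (1 − q)^18, where q is the late risk per participant. The documents do not give q. For assumed values of 1%, 2%, 5% and 10%, the chance is 17%, 31%, 60% and 85%. These figures show only how strongly the result depends on q.

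**Day 7 to 28 rates.** These are unchanged when event-free participants are assessed through Day 28. They can be slightly too high if someone stops CRS assessments early and has a late first event, because that person stays at risk until the event.

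**The case against.** The strongest reply is that the SAP already shows the intended scope. Table 2.2.4.1 in Appendix A is titled as CRS-free survival by Day 28 after IEC therapy. Onset and duration of ICANS and of CRS each have a Day 28 table and a second table for the lifetime of the study (2.2.2.1 and 2.2.2.2; 2.2.3.1 and 2.2.3.2). CRS-free survival has only the Day 28 table. Its landmark rates and its censoring also stop at Day 28. A programmer who took the scope from the table title would not produce the collapse.

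This stands as evidence of intent. It does not close the gap. A table title does not say how to code a death on Day 100, Appendix A describes its lists as guidelines, and the title of Figure 4.1.1 carries no time limit. The derivation text states a rule for anyone with an event, and that rule gives the wrong result.

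It is also fair to say that no test is attached to this analysis, that CRS-free survival is not in the visible endpoint tables, and that the chance of a false median rests on an assumed risk. These points limit the weight of the concern, not its correctness.

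**Conclusion.** Wrong as written, and minor. A false median needs three things together: the text of 7.3.4 is followed literally, the Day 28 estimate is above 50%, and at least one first event falls after the last censoring time, about Day 28 to 30. When they coincide, zero at the last late event and a finite median follow from arithmetic. The example's event times are assumed.

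The effect is confined to descriptive outputs: the median, the event count and the tail of Figure 4.1.1. The primary Z-test is unaffected, and the Day 7 to 28 rates essentially so.

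Three stronger readings are tempting and are not supported:
- That the sponsor means to count events to Day 180. The table structure in Appendix A points the other way.
- That the reported median will be wrong, or wrong with a known probability. The documents give no late-event rate.
- That the chance can be worked out for each IEC product group in Part 1. SAP 5.2 names three groups without sizes. The 10 participants with ALL in SAP 3.1 are a disease count, and 62 is the whole of Part 1.

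**What to change.** In SAP 7.3.4, state that only events on or before Day 28 after IEC therapy count. State also that participants with no event by then, including those with a later first event, are censored at their last CRS assessment by Day 28. End Figure 4.1.1 at Day 28, and report the median as not reached when the Day 28 estimate is above 50%. The text and the figure then match Table 2.2.4.1. The cost is about one sentence in the SAP and one line of programming, with no new data.
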